5.2.4.2 Adverse event collection and reporting

5.2.4.2.1 AE Collection

The investigator shall maintain and keep detailed records of all AEs in the patient files. The following must be collected and documented on the appropriate CRF(s) by the investigator:

- From signing the informed consent onwards until the individual patient's end of program (16 weeks after last dose of spesolimab, or at the time of withdrawal of participation): all AEs (serious and non-serious) and all AESIs.
- After the individual patient's end of program: the investigator does not need to actively monitor the patient for new AEs but should only report any occurrence of cancer and program drug-related SAEs and program drug-related AESIs of which the investigator may become aware of by any means of communication, e.g. phone call. Those AEs should however not be reported in the CRF.
- Upon patient re-entry into the program, the patient should be re-evaluated to ensure that eligibility criteria are still met and the overall program is still running in order to assess AEs (serious and non-serious) and AESIs.

Vital Status Data Collection

Patients who withdraw their consent to program participation, who agree to be contacted further but do not agree to physical visits, should be followed up as described in section [3.2.4.2](#), withdrawal from program treatment. Thus, for patients who withdraw their consent

but agree to be contacted by phone for a last follow-up assessment at 16 weeks after last drug intake, the investigator must report any occurrence of cancer, all deaths / fatal AEs regardless of relationship, and program drug-related SAEs and and program drug-related AESIs the investigator becomes aware of.

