Window			±1d	±1d	±7d	±7d
Informed consent	X					
Demographics	X					
Medical history	X					

Proprietary confidential information © 2022 Boehringer Ingelheim International GmbH or one or more of its affiliated companies

Trial Period	Screening		Treatment		Follow-up Period	
	V1 ¹	V2 ¹	V3 ²	V4	V5	V6/EoS ³
Visit						
Week [REDACTED] ²						
Week [REDACTED] ²						
Window			±1d	±1d	±7d	±7d
Baseline condition	X					
Physical examination	X	X	(X) ⁵	(X) ⁵	(X) ⁵	(X) ⁵
Vital signs	X	X	(X) ⁵	(X) ⁵	(X) ⁵	(X) ⁵
Pregnancy test ⁴	X					
Infection testing ⁶	X					
Safety laboratory tests (Local lab) ⁷	X		(X) ⁵	(X) ⁵	(X) ⁵	(X) ⁵
Nucleic acid testing	X					
COVID-19 symptoms		(X)	(X)	(X)	(X)	(X)
Review of in-/exclusion criteria	X	X				
IRT transaction	X	X	X			
Dispense/administration study drug		X	X			
Adverse events	X	X	X	X	X	X
Concomitant therapy	X	X	X	X	X	X
[REDACTED]						
Study Completion						X

Abbreviations: EoS: end of study; IRT: Interactive Response Technology; V: Visit.

- 1: Visit 1 and Visit 2 can be on the same day. If V1 and V2 is performed on the same day, the procedures do not need to be repeated.
- 2: V3 is an additional visit. There's a possibility that patient will receive [REDACTED] of spesolimab at V3 [REDACTED] if his flare symptoms persist after the [REDACTED] dose. If in that case, the visit schedule will be changed to approximately at [REDACTED] after initial dose of spesolimab.
- 3: Should a patient prematurely discontinue from the treatment; every effort should be made to keep the patient in the trial and complete all of the remaining study visits. If a patient is not willing to follow the whole visit schedule, the EOS Visit (Visit 6) should be conducted at [REDACTED] weeks after the last spesolimab administration at a minimum. If patients refuse to return to the study site, early EoS visit should be completed at the timing of prematurely discontinuation and then at least safety information should be collected by phone at [REDACTED] weeks after the last spesolimab administration.
- 4: Only applicable for women of childbearing potential.
- 5: Physical examination, vital signs and safety laboratory test shown with parentheses "(X)" are optional and will be performed according to standard clinical practice and when deemed appropriate by the investigator.

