If a patient wants to discontinue the participation in the program, the investigator should request that the patient consent to be contacted, at least by phone, for a final follow-up assessment at 16 weeks after last drug intake. Where possible, any new or changes in previously reported AEs and concomitant therapies should be recorded at this assessment, as indicated in section [6.1.3](#). Specific information to be collected at the [REDACTED]-week assessment in patients who have discontinued triam medication or assessment is detailed in section [5.2.4.2.1](#).

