3.2.4.2 Withdrawal of consent to program participation

Patients may withdraw their consent to program participation at any time without the need to justify the decision.

If a patient wants to withdraw consent, the investigator should be involved in the discussion with the patient and explain the difference between treatment discontinuation and withdrawal of consent to program participation, as well as explain the options for continued follow-up after treatment discontinuation, please see Section [3.2.4.1](#) above. This discussion, as well as the patient’s decision, should be well documented in the source.

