5.2.4.2.2 AE reporting to the sponsor and timelines

The investigator must report SAEs, AESIs, and non-serious AEs which are relevant for the reported SAE or AESI, on the BI SAE form to the sponsor's unique entry point within 24 hours of becoming aware of the event. The country-specific process will be specified in the ISF. The same timeline applies if follow-up information becomes available. In specific instances, the investigator could inform the sponsor upfront via telephone. This does not replace the requirement to complete and send the BI SAE form.

With receipt of any further information to these events, a follow-up SAE form has to be provided. For follow-up information the same rules and timeline apply as for initial information.

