6.1.3 Follow up period and program completion

Patients will visit the treating physician at approximately week [redacted], week [redacted] and week [redacted] after [redacted] drug administration. If the patient requires [redacted] of spesolimab, visits will be re-scheduled based on the date of the last [redacted], i.e., patients will visit the treating physician at approximately week [redacted], week [redacted], week [redacted], and week [redacted] after initial dose of spesolimab. Additional visits within the [redacted]-week follow-up period can be planned according to standard clinical practice. Visits not including the mandatory presential visits at screening (baseline) and [redacted] week after (any) administration of spesolimab, may also be conducted by phone or video if judged appropriate by the treating physician. At all visits any new or changes in previously reported AEs and concomitant therapies will be recorded in the patient's chart and eCRF.

Patient's participation in the program will end after conclusion of the [redacted]-week follow-up period after the last [redacted] / drug administration. The Trial (Program) Completion eCRF page will be completed at this time.

A patient will be considered lost to follow-up if the treating physician is not able to contact the patient despite multiple attempts. Every effort must be made to contact the patient and be documented in the patient's chart.

[figure not shown]
If a patient experiences a new GPP flare (following the resolution of a previous flare with spesolimab treatment) after the [redacted]-week follow-up period, the patient may re-enter in the program with the same patient number and be treated again with spesolimab, providing eligibility criteria are still met and the overall program is still running. The same dosing and follow-up requirements apply as for the previous flare.

In the situation that a patient experiences a new GPP flare within the [redacted]-week follow-up period and the physician wishes to treat this new flare with spesolimab, eligibility needs to be assessed and agreed upon with the BI clinical team.

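### Protocol 5.2.4.2.1 and 3.2.4.1 with 6.1.3 contradict each other on which adverse events are captured at the 16-week call after a patient withdraws from participation

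*Protocol*

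**What the plan says.** **Narrow scope.** Protocol 5.2.4.2.1 has all AEs, serious or not, documented in the CRF from consent until the patient's end of program. That end is 16 weeks after the last dose "or at the time of withdrawal of participation". For events that become known after the end of program it adds: "Those AEs should however not be reported in the CRF". Its paragraph on vital status covers patients who withdraw consent but agree to a call at 16 weeks. For them, "the investigator must report any occurrence of cancer, all deaths / fatal AEs regardless of relationship, and program drug-related SAEs", together with drug-related AESIs.

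**Wide scope.** Protocol 3.2.4.1 describes a call at the same time point for a patient who wants to leave the program: "Where possible, any new or changes in previously reported AEs and concomitant therapies should be recorded at this assessment", in the manner of 6.1.3. Section 6.1.3 says: "At all visits any new or changes in previously reported AEs and concomitant therapies will be recorded in the patient's chart and eCRF".

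**Link between them.** Protocol 3.2.4.2, on consent withdrawal, sets no AE scope. It has the investigator explain the difference between stopping treatment and withdrawing consent, "as well as explain the options for continued follow-up after treatment discontinuation, please see Section" 3.2.4.1. Section 3.2.4.1 cites 6.1.3 for recording and, in its next sentence, 5.2.4.2.1 for the specific information to collect.

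**Analysis.** The endpoints in Protocol 2.1.2 and 2.1.3 are the occurrence of treatment-emergent AEs, SAEs and AESIs. Section 7.1.1 counts events up to 16 weeks after the last dose. SAP Table 6.1: 1 ends the on-treatment period at the earliest of last treatment + 112 days, the end of study visit, or screening for the next flare. SAP 7.8.1 censors at the earliest of death, the last contact date on the EoS page, or the end of that period. Neither document has a rule for withdrawal of consent.

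**The concern.** AE occurrence is the primary endpoint of this program, and collecting safety data is its stated secondary aim. At this one contact, two sites can follow the protocol in good faith and deliver different data. A site that works from 5.2.4.2.1 filters by causality, and it drops non-serious events unless they are drug-related AESIs or cancers. A site that works from 3.2.4.1 enters everything it hears. The endpoint definitions know no such filter.

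The percentage of treated patients with an event can then only be too low. The exposure-adjusted rate, which SAP 7.8.1 uses for the primary endpoint, depends also on the date at which time at risk ends. Neither document ties that date to the date on which complete AE collection ended.

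**Working it through.** **Step 1: the texts side by side**

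| Question | 5.2.4.2.1 | 3.2.4.1 with 6.1.3 |
|---|---|---|
| Who | Withdrew consent, accepts the call | Leaves participation, accepts the call; 3.2.4.2 sends consent withdrawers here |
| When | 16 weeks after last drug intake | 16 weeks after last drug intake |
| Which AEs | Cancers, deaths and fatal AEs, drug-related SAEs and AESIs | Any new or changed AE, where possible |
| CRF | All-AE collection ends at withdrawal; later reports stay out | Chart and eCRF |

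The third row can be read as a mandatory minimum plus best effort. The fourth row cannot be reconciled in that way, because no exemption from the CRF exclusion is stated for this call.

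**Step 2: what goes missing under 5.2.4.2.1.** Lost are non-fatal, non-cancer SAEs and AESIs judged unrelated, and non-serious AEs other than cancers and drug-related AESIs. If the CRF exclusion is applied strictly, nothing from the call enters the CRF.

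**Step 3: illustration of size.** The plan gives no figure to reproduce. Its windows agree: 16 × 7 = 112 days.

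Inputs from Protocol 1.2.3 (spesolimab arm of the earlier randomised trial): SAE 14.3% at week 1 and 25.7% at week 12; any AE 77.1% and 91.4%.

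Assumptions not in the documents: a single dose; the hazard after week 1 holds to Day 112; a share *w* = 5, 10 or 20% withdraw and accept the call; withdrawal on day *d* = 8, 29 or 57; a share *c* = 10, 30 or 50% of their later events is captured.

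SAE hazards:
- h1 = −ln(1 − 0.143)/7 = 0.02205 per day, Days 0–7
- h2 = [ln(1 − 0.143) − ln(1 − 0.257)]/77 = 0.00185 per day, after Day 7
- 16-week risk = 1 − exp(−7·h1 − 105·h2) = 29.5%
- Mean time to first event or Day 112 (area under the event-free curve) = 88.3 days

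A single constant hazard fitted to 25.7% would give only 2.4% at week 1 against the 14.3% reported, so two pieces are needed.

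Central case (*w* = 10%, *d* = 29, *c* = 30%):
- Withdrawers' counted risk = 1 − exp(−7·h1 − 22·h2 − 0.3·83·h2) = 21.4%
- Crude percentage = 0.9 × 29.46 + 0.1 × 21.44 = 28.7%, a relative loss of 2.7%
- Clock runs on to the call: mean time = 0.9 × 88.26 + 0.1 × 91.70 = 88.6 days; rate = 0.2866/88.6 against 0.2946/88.26, 3.1% lower
- Events and clock both stop at withdrawal: withdrawers' risk to Day 29 = 17.7%, pooled 28.28%; mean time = 0.9 × 88.26 + 0.1 × 24.96 = 81.9 days; rate 3.4% higher

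Any TEAE, same formulas: h1 = 0.2106, h2 = 0.0127, 16-week risk 94.0%. Withdrawers' counted risk is 87.4%. Crude = 0.9 × 93.98 + 0.1 × 87.39 = 93.3%, a relative loss of 0.7%. The rate is 2.7% lower if run on and 4.3% higher if stopped.

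| Relative change, whole grid | SAE | Any TEAE |
|---|---|---|
| Crude percentage | −9.1% to −0.6% | −2.9% to −0.1% |
| Crude, no call data at all | −10.2% to −1.3% | −3.5% to −0.3% |
| Rate, clock runs on | −10.5% to −0.7% | −12.2% to −0.4% |
| Rate, both stop | +1.1% to +10.0% | +1.1% to +14.0% |

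The rate rises when both stop because events are front-loaded: the person-time removed is the low-hazard part.

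**The case against.** **The scopes are compatible.** One text says must, the other says where possible. This stands for the reporting minimum. It does not say whether the best-effort events go into the CRF, where the two sections conflict.

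**Section 3.2.4.1 is about stopping treatment.** Its title suggests so. But its paragraph speaks of leaving the program, and 3.2.4.2 sends consent withdrawers to it.

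**SAEs reach the sponsor anyway.** This stands for safety reporting. Section 5.2.4.2.2 says "The investigator must report SAEs, AESIs, and non-serious AEs which are relevant for the reported SAE or AESI, on the BI SAE form", with no causality limit. A reader might infer that unrelated SAEs are lost to the sponsor altogether, and the documents do not support that. The SAE form does not settle CRF or endpoint capture, and it covers non-serious AEs only when they bear on a reported SAE or AESI.

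**Limited collection after withdrawal may be deliberate.** That is a legitimate choice, but 3.2.4.1 then asks for the opposite. A single call as late as 104 days (about 15 weeks) after withdrawal also relies on recall for non-serious events, which is a real limit of the wider scope.

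**The flow chart footnote.** Footnote 3 of the flow chart in 3.1 says "early EoS visit should be completed at the timing of prematurely discontinuation and then at least safety information should be collected by phone". A reader might take this as a third scope for the same call, and as proof that an early EoS visit closes the SAP period for these patients. It concerns premature discontinuation of treatment and does not mention withdrawal of consent, so it shows neither.

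**Conclusion.** The contradiction is in current text and concerns one defined group: patients who withdraw from participation and accept the 16-week call. It is not a matter of silence. Section 5.2.4.2.1 taken alone closes the CRF at withdrawal, and 3.2.4.1 with 6.1.3 opens it. Following 5.2.4.2.1 leaves endpoint events uncounted by causality and seriousness, which neither the endpoints nor 7.1.1 provides for.

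A reader might infer that the exposure-adjusted rate is biased downward. That holds only if the call is logged as EoS or last contact, so that risk time runs on. If the EoS page carries the withdrawal date, events and time stop together, and the rate may instead be slightly high. The direction is not fixed.

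The actual size is unknown: withdrawal share, timing and captured share are all assumed. In the central case the loss is about 2.7% relative for the SAE percentage and 0.7% for any TEAE, and rates shift by a few percent in either direction. The program is single-arm and descriptive with no hypothesis test, so the effect is on completeness of the safety profile. Minor.

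**What to change.** **Protocol.** Reconcile 5.2.4.2.1 with 3.2.4.1 and 6.1.3. Within the consent the patient has given, record in the eCRF at this call all AEs, SAEs and AESIs with onset up to 16 weeks after the last dose, whatever the relationship. State that the CRF exclusion after end of program does not apply to this call.

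**SAP Table 6.1: 1 and 7.8.1.** For these patients, end countable events and time at risk on the same date: the call date, at most last dose + 112 days, if all AEs were collected there; otherwise the withdrawal date. Report how many patients were stopped before 16 weeks. Wider collection alone would not reach the endpoint if an earlier EoS date had already closed the period.

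**Cost.** The protocol change is an amendment, which under 8.1 needs ethics committee and authority approval. The call already takes place, so sites face a somewhat longer call and a few more entries. Recall error for non-serious AEs remains, and counting risk time to the call date then includes some under-ascertained time. Stopping at withdrawal where collection was incomplete can raise the rate a little, hence the count of early stops. SAP section 3 places three trials under this SAP (1368-0073, 1368-0077 and 1368-0109), so the change also touches the other two. If no amendment is wanted, the SAP rule alone removes the run-on case but leaves the contradiction and the shortened window.

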5.2.4.2.2 AE reporting to the sponsor and timelines

The investigator must report SAEs, AESIs, and non-serious AEs which are relevant for the reported SAE or AESI, on the BI SAE form to the sponsor's unique entry point within 24 hours of becoming aware of the event. The country-specific process will be specified in the ISF. The same timeline applies if follow-up information becomes available. In specific instances, the investigator could inform the sponsor upfront via telephone. This does not replace the requirement to complete and send the BI SAE form.

With receipt of any further information to these events, a follow-up SAE form has to be provided. For follow-up information the same rules and timeline apply as for initial information.

5.2.4.2.3 Information required

All (S)AEs, including those persisting after individual patient's end of program, must be followed up until they have resolved, have been assessed as "chronic" or "stable", or no further information can be obtained.

5.2.4.2.4 Pregnancy

In rare cases, pregnancy might occur in a clinical program. Once a patient has been enrolled in the clinical program and has taken program medication, the investigator must report any drug exposure during pregnancy (DEDP) in a program participant immediately (within 24 hours) by means of Part A of the Pregnancy Monitoring Form to the sponsor's unique entry point.

The outcome of the pregnancy associated with the drug exposure during pregnancy must be followed up and reported to the sponsor's unique entry point on the Pregnancy Monitoring Form for Clinical Studies (Part B).

The ISF will contain the Pregnancy Monitoring Form for Clinical Studies (Part A and B).

As pregnancy itself is not to be reported as an AE, in the absence of an accompanying SAE and/or AESI, only the Pregnancy Monitoring Form for Clinical Studies and not the SAE form is to be completed. If there is an SAE and/or AESI associated with the pregnancy an SAE form must be completed in addition.

6. INVESTIGATIONAL PLAN

6.1 DETAILS OF PROGRAM PROCEDURES AT SELECTED VISITS

6.1.1 Screening period

After informed consent, patients considered for this program will undergo an eligibility evaluation. Laboratory tests, must be conducted locally to ensure patients meet the inclusion and exclusion criteria described in sections [3.2.2](#) and [3.2.3](#), which include:

- Liver function tests (AST, ALT and alkaline phosphatase)
- Complete blood count, with differential
- Pregnancy (urine or blood) test in women of childbearing potential
- TB test, to rule out active disease
 - In accordance with details in section [4.2.1.1](#), if TB test results are not available at the time of [REDACTED], patients may receive treatment (provided they meet all other inclusion/exclusion criteria) as long as the investigator has ruled out active disease based on available documented history (i.e. negative for active TB) within 3 months prior to [REDACTED].
- Possible HIV and viral hepatitis tests, to rule out active disease in presence of clinical signs or suspicion
 - If HIV and viral hepatitis test results are not available at the time of [REDACTED], patients may receive treatment (provided they meet all other inclusion/exclusion criteria) as long as the investigator has ruled out active disease based on available documented history (i.e. negative for HIV and viral hepatitis) within 3 months prior to [REDACTED].

Once consent is obtained, the patient is considered to have started the screening process and is assigned a unique patient number in the IRT system. The patient is to be recorded on the enrolment log and registered in the IRT system as a screened patient. All patients who are screened must be registered in the IRT system.

Demographics, baseline conditions (including any findings of the physical examination and vital signs evaluation) and concomitant therapies will be recorded in the eCRF.

If the patient meets all eligibility criteria, [REDACTED] of spesolimab may proceed immediately.

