3. DESCRIPTION OF DESIGN AND PROGRAM POPULATION

3.1 OVERALL PROGRAM DESIGN AND PLAN

This is an open-label, multi-centre, single-arm trial, designed to provide early access to spesolimab, for patients with GPP presenting with a flare and for whom no satisfactory authorised alternative therapy exists and who are unable to participate in a clinical trial, as assessed by the treating physician.

After signing informed consent and if all eligibility criteria are met, patients will receive a [REDACTED] spesolimab. If deemed necessary by the treating physician (i.e. if the flare symptoms persist), a [REDACTED] spesolimab may be administered [REDACTED] after the initial [REDACTED].

If [REDACTED] is administered, then patients will visit the treating physician approximately at week [REDACTED], week [REDACTED] and week [REDACTED]. If a [REDACTED] may be given, then the dates that patients will visit the treating physician is changed to approximately at [REDACTED] [REDACTED] after initial dose of spesolimab. Please refer to section [6.1](#) for details on the program visit procedures. Patient's participation in the program will end after conclusion of the [REDACTED]-week follow-up period after the last [REDACTED] / drug administration.

If a patient experiences a new GPP flare (following the resolution of a previous flare with spesolimab treatment) after the [REDACTED]-week follow-up period the patient may re-enter in the program and be treated again with spesolimab, providing eligibility criteria are still met and the overall program is still running. The same dosing and follow-up requirements apply as for the previous flare.

In the situation that a patient experiences a new GPP flare within the [REDACTED]-week follow-up period and the physician wishes to treat this new flare with spesolimab, eligibility needs to be assessed and agreed upon with the BI clinical team.

The enrolment of patients for the program will stop at the time spesolimab becomes commercially available or 6 months after marketing authorization for treatment of GPP in China (whichever is earlier). The overall program will close when the last patient completes the follow up period after the last [REDACTED] of spesolimab or if any other reason listed in section [3.2.4.3](#) is met.

Below is suggested flow chart for patient visit.

Flow Chart

Trial Period	Screening	Treatment		Follow-up Period		
Visit	V1 ¹	V2 ¹	V3 ²	V4	V5	V6/EoS ³
Week [REDACTED]) ²						
Week [REDACTED]) ²						

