- 6: Infection testing includes tuberculosis, viral hepatitis tests (at least to include anti-hepatitis B core antibody, hepatitis B surface antigen, hepatitis C virus antibody) and HIV assessments.
- 7: Safety laboratory tests at screening visit (Visit 1) include liver function test (at least to include AST/GOT, ALT/GPT, alkaline phosphatase, and total bilirubin), haematology test (at least to include complete blood count with differential).

[REDACTED]

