3.2.3 Exclusion criteria

1. Women who are pregnant, nursing, or who plan to become pregnant while in the program.
 - a) Women who stop nursing before study drug administration do not need to be excluded from participating; they should refrain from breastfeeding for 16 weeks after the last spesolimab [REDACTED].
2. Severe, progressive, or uncontrolled hepatic disease, defined as >3-fold Upper Limit of Normal (ULN) elevation in AST or ALT or alkaline phosphatase, or >2-fold ULN elevation in total bilirubin.
3. Active systemic infections (fungal and bacterial disease) during the last 2 weeks prior to drug administration, as assessed by the treating physician.
4. Increased risk of infectious complications (e.g. recent pyogenic infection, any congenital or acquired immunodeficiency (e.g. HIV), past organ or stem cell transplantation), as assessed by the treating physician.
5. Relevant chronic or acute infections, including active tuberculosis (TB), HIV infection or viral hepatitis at the time of drug administration.
 - a) Patients should be evaluated for TB infection prior to initiating treatment with spesolimab.

¹A woman is considered of childbearing potential (WOCBP), i.e. fertile, following menarche and until becoming post-menopausal unless permanently sterile.

Permanent sterilisation methods include hysterectomy, bilateral salpingectomy and bilateral oophorectomy.

Tubal ligation is NOT a method of permanent sterilisation.

A postmenopausal state is defined as no menses for 12 months without an alternative medical cause.

b) Anti-TB therapy should be considered, in accordance with local guidelines, prior to initiating spesolimab in patients with latent TB or a history of TB.

6. History of allergy / hypersensitivity to systemically administered spesolimab or its excipients.

7. Any documented active or suspected malignancy or history of malignancy within 5 years prior to screening, except appropriately treated basal or squamous cell carcinoma of the skin or in situ carcinoma of uterine cervix.

8. Immediate life-threatening flare of GPP requiring intensive care treatment according to the investigator's judgement. Life-threatening complications include cardiovascular / cytokine driven shock, pulmonary distress syndrome, or renal failure.

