A suitable TB test, according to local regulations will be performed at screening. If the result is positive, the patient may participate in the program if further work up (according to local practice/guidelines) establishes conclusively that the patient has no evidence of active tuberculosis. Active TB patients must be excluded. If the presence of latent tuberculosis is established, then treatment should have been initiated and maintained according to local country guidelines. If the TB test results are not available at the time of [REDACTED], these patients may receive treatment (provided they meet all other inclusion/exclusion criteria) as long as the investigator has ruled out active disease based on available documented history (i.e. negative for active TB) within 3 months prior to [REDACTED].

Malignancies

In case of occurrence of malignant neoplasm other than appropriately treated basal cell carcinoma or squamous cell carcinoma of the skin or in situ carcinoma of uterine cervix, treatment discontinuation is to be a consideration if deemed clinically appropriate by the investigator. In addition, diagnostics and treatment are to be initiated according to local standard of care.

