8.3.1 Source documents

In accordance with regulatory requirements, the investigator should prepare and maintain adequate and accurate source documents and program records that include all observations and other data pertinent to the investigation on each program patient. Source data as well as reported data should follow the "ALCOA principles" and be attributable, legible, contemporaneous, original and accurate. Changes to the data should be traceable (audit trail). Data reported on the CRF must be consistent with the source data or the discrepancies must be explained.

The current medical history of the patient may not be sufficient to confirm eligibility for the program and the investigator may need to request previous medical histories and evidence of any diagnostic tests. In this case, the investigator must make one documented attempt to retrieve previous medical records. If this fails, a verbal history from the patient, documented in their medical records, would be acceptable.

If the patient is not compliant with the protocol, any corrective action e.g. re-training must be documented in the patient file.

For the CRF, data must be derived from source documents, for example:

- Patient identification: gender, year of birth (in accordance with local laws and regulations).
- Patient participation in the program (substance, program number, patient number, date patient was informed).
- Dates of patient's visits, including dispensing of program medication.
- Medical history (including program indication and concomitant diseases, if applicable).
- Medication history.
- Adverse events and outcome events (onset date (mandatory), and end date (if available)).
- Serious adverse events (onset date (mandatory), and end date (if available)).
- Concomitant therapy (start date, changes).
- Originals or copies of laboratory results and other imaging or testing results, with proper documented medical evaluation (in validated electronic format, if available).
- Completion of patient's participation in the program (end date; in case of premature discontinuation document the reason for it).

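### Section 6.1.1 ties HIV and viral hepatitis testing to clinical signs or suspicion, while the flow chart lists the tests for every patient at Visit 1 and exclusion 5 is not limited to symptomatic infection

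*Protocol*

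**What the plan says.** Four parts of the protocol bear on who is tested for HIV and viral hepatitis before dosing.

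- **Section 6.1.1 (Screening period).** The lead-in says that local laboratory tests must be done to confirm eligibility. The list that follows includes "Possible HIV and viral hepatitis tests, to rule out active disease in presence of clinical signs or suspicion". A sub-bullet covers dosing when results are not yet available: the investigator must have ruled out active disease "based on available documented history (i.e. negative for HIV and viral hepatitis) within 3 months prior to" dosing.
- **Section 3.1 (flow chart).** The chart is introduced with "Below is suggested flow chart for patient visit". Infection testing carries a plain X at Visit 1. Footnote 6 defines it as tuberculosis, "viral hepatitis tests (at least to include anti-hepatitis B core antibody, hepatitis B surface antigen, hepatitis C virus antibody) and HIV assessments". Footnote 5 reserves optional status for items in parentheses: "Physical examination, vital signs and safety laboratory test shown with parentheses". Infection testing is not marked that way.
- **Section 3.2.3, criterion 5.** This excludes "Relevant chronic or acute infections, including active tuberculosis (TB), HIV infection or viral hepatitis at the time of drug administration". Sub-items (a) and (b) add instructions for TB only.
- **Section 8.3.1.** Eligibility must be supported by source evidence, and missing records do not make a patient eligible. Documented verbal feedback from the patient counts as a record. After one documented failed attempt to retrieve earlier records, the section adds: "If this fails, a verbal history from the patient, documented in their medical records, would be acceptable".

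TB is handled differently from HIV and hepatitis. Section 6.1.1 lists the TB test without a suspicion condition, and section 4.2.1.1 states "A suitable TB test, according to local regulations will be performed at screening".

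**The concern.** A test ordered only on signs or suspicion cannot find a silent infection, yet the exclusion it serves is not confined to symptomatic disease. Two sites could follow the same protocol in good faith and screen differently, one testing every patient and the other testing only those with signs.

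The protocol itself shows why this matters. Table 1.4:1 names exclusion of patients with HIV or viral hepatitis among its mitigations for infection risk. Section 5.2.4.1.4 includes HBV reactivation and HCV progression among the opportunistic infections that count as AESIs. After dosing, safety laboratory tests are optional (flow chart footnote 5, section 5.2.3), so a carrier missed at screening may have no scheduled liver test later. A patient who re-enters with a new flare must be re-evaluated for eligibility, so the same question returns at each re-entry.

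**Working it through.** There is no plan figure to reproduce. The check is a comparison of texts, followed by simple counts.

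**Step 1. Which infections named in exclusion 5 does 6.1.1 test without a condition?**

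| Infection in exclusion 5 | Section 6.1.1 | Flow chart, Visit 1 |
|---|---|---|
| TB | tested, no suspicion condition | plain X |
| HIV | only on signs or suspicion | plain X |
| Viral hepatitis | only on signs or suspicion | plain X |

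Section 6.1.1 tests 1 of 3 unconditionally and 2 of 3 conditionally. The flow chart lists 3 of 3.

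**Step 2. The same count by component of footnote 6, for a patient with no signs.** The components are TB, anti-HBc, HBsAg, HCV antibody and HIV, which makes 5. Section 6.1.1 calls for 1 of 5 (TB) and the flow chart for 5 of 5. Footnote 6 names no HIV assay. If HIV is left out for that reason, the counts become 1 of 4 and 4 of 4, and the gap remains.

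**Step 3. Does any other text settle which rule applies?**

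- *The word suggested before the flow chart.* It weakens the chart's authority but does not reconcile footnote 6, which sets a minimum panel, with a bullet that makes the tests only possible.
- *The 3-month rule.* It sits beneath the conditional bullet and speaks of results that are not available. It can be read as covering a patient who was never tested, or only a patient whose ordered test is still pending.
- *Section 8.3.1.* It demands evidence but accepts a documented verbal history. A patient unaware of an infection would report none.

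None of these states whether a patient without signs must be tested.

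**Step 4. A smaller mismatch in the same list.** Exclusion 2 uses four liver analytes: AST, ALT, alkaline phosphatase and total bilirubin. The liver bullet in 6.1.1 names 3 of the 4 and omits total bilirubin. Footnote 7, section 5.2.3 and exclusion 2 all name it, so this is editorial and carries no weight in the conclusion.

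**Step 5. Size in patients.** The expected number of undetected carriers dosed would be the number of patients without signs, times the share left untested, times the prevalence of silent infection. The protocol gives none of the three and sets no recruitment goal, so no number is offered.

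**The case against.** The strongest reply is that existing text already blocks most of the harm. The lead-in to 6.1.1 says tests must be done to confirm eligibility. In ordinary language an untested patient has no available result, so the 3-month documented-negative rule would apply. Section 8.3.1 says missing records do not confer eligibility. These safeguards are real, and a careful site could read them together as requiring proof of negative status from everyone. A less strict reading is equally open, however, because the 3-month rule hangs from a conditional bullet and 8.3.1 accepts a verbal history.

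A second reply is that TB may be treated differently on purpose, since sub-items (a) and (b) of exclusion 5 give TB its own instructions. That explains the extra handling of TB. It does not make sign-triggered testing adequate for infections that the same criterion excludes.

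A third reply is that exclusion 5 is qualified by the word relevant and does not mention symptoms. Both points are correct. But the criterion names HIV infection and viral hepatitis as included, and judging relevance requires knowing the patient's status.

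A fourth reply is that the conflict could be removed the other way, by making the flow chart conditional, and that speed matters in an access program for a potentially life-threatening condition. This is a genuine choice for the sponsor. Conditional testing would make the two texts agree but would leave silent infection undetected, against the mitigation stated in Table 1.4:1.

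It also stands that no endpoint, analysis set or statistical figure is affected, and that differing practice between sites is a possibility, not something observed.

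**Conclusion.** The concern holds. Section 6.1.1 and the flow chart give different rules for the same tests, and no other text says which prevails. For a patient without signs the difference is 1 of 5 components against 5 of 5. The conflict is certain on the wording. The harm is possible and partly mitigated, and its frequency cannot be derived from the documents. The conclusion assumes that exclusion 5 is meant to apply to infection without symptoms, which is how it reads: the word active is attached to tuberculosis, and nothing confines HIV or hepatitis to symptomatic cases. This is a point the sponsor should correct for patient safety and uniform screening. It does not bear on the validity of the descriptive analyses.

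**What to change.** In section 6.1.1, remove the word that makes the HIV and hepatitis tests optional and the condition on signs or suspicion. Require anti-HBc, HBsAg, HCV antibody and an HIV test for every patient at screening, in line with footnote 6 and with the way 6.1.1 already treats TB. Keep the documented negative history within 3 months as the only route to dosing without a result, and say that it applies whether a test is pending or was never ordered. In the same edit, add total bilirubin to the liver bullet.

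The change touches two bullets and adds no procedure, because the tests are already in the flow chart. As a protocol amendment it needs ethics committee and competent authority approval under section 8.1. The clinical cost is that a patient in flare with no documented negative history within 3 months must wait for the local result. The change settles who is tested. It does not settle how an isolated positive anti-HBc should be judged against exclusion 5, and the sponsor may wish to state that as well.
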